8.2.1 Safety Data

To minimize the effect of dropouts and missing data, the study period will be divided into time intervals for statistical analysis of safety.

Unsolicited adverse events: these events will be reported from the date of signed informed consent to Day 14 and from Day 15 to study termination (for SAEs, Medically Attended AEs, NOCDs and AESIs).

Solicited adverse events, the solicited study period (Days 1-14) after vaccination will be divided into these intervals: 30 min, Days 1-4 (without 30 min), Days 5-8, Days 1-8 (without 30 min), Days 8-14 and Days 1-14 (without 30 min).

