13.2 Solicited Local and Systemic Adverse Events

For details, refer to [section 7.1.1](#) of the protocol.

Plausible observations are those with non-missing values other than those “Not done/unknown” or implausible values (see [section 6.3](#)). Implausible measurements will be excluded from summary tables but included in listings.

Solicited adverse events will be recorded at 30 minutes and Day 1 directly into the clinical database; and, from Day 2 to Day 14 in the subject diaries.

The analyses of solicited adverse events will be performed separately at these intervals: 30 minutes, Days 1-4 (without 30 minutes), Days 5-8, Days 8-14, Days 1-8 (without 30 minutes) and Days 1-14 (without 30 minutes). In addition, solicited AEs ongoing after day 14 will be presented as unsolicited AEs.

In the case of local AEs, for grades 1 to 3 (i.e., Mild to Severe), refer to Appendix A in the protocol. Grade 4 (Potentially Life Threatening) will be defined as follows (see also Appendix 2):

- Pain: Emergency room (ER) visit or hospitalization.
- Tenderness: ER visit or hospitalization.
- Erythema/Redness: Necrosis or exfoliative dermatitis.
- Induration/Swelling: Necrosis.

(Guidance for Industry Toxicity Grading Scale for Healthy Adult and Adolescent Volunteers Enrolled in Preventive Vaccine Clinical Trials, USDA, 2007).

All summary tables will include the number and percent of subjects with solicited adverse events by dosage group and time interval as well as overall.

Summary tables of solicited adverse events by severity and maximal severity will be created. Summary tables showing the occurrence of any local or systemic solicited adverse event will also be created.

The solicited local adverse events include these evaluations at the injection site: erythema, induration, swelling and pain. For erythema, induration and swelling recorded originally as diameters (mm), these categories will be used to summarize the data: None (0 mm), Grade 0 (<25 mm), Any (\geq 25 mm) with subcategories for Mild (25-50 mm), Moderate (51-100 mm) and Severe ($>$ 100 mm).

In the case of systemic AEs, for grades 1 to 3 (i.e., Mild to Severe), refer to Appendix B in the protocol. Grade 4 (Potentially Life Threatening) will be defined as follows (see also Appendix 3):

- Fever: >40 C (>104 F)
- Chills: ER visit or hospitalization
- Loss of Appetite: ER visit or hospitalization
- Nausea: ER visit or hospitalization for hypotensive shock

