- Vomiting: ER visit or hospitalization for hypotensive shock
- Diarrhea: ER visit or hospitalization
- Generalized Myalgia: ER visit or hospitalization
- Generalized Arthralgia: ER visit or hospitalization
- Headache: ER visit or hospitalization,
- Fatigue: ER visit or hospitalization,
- Generalized Rash, ER visit or hospitalization Urticaria: ER visit or hospitalization.

Body temperature will be broken down by route of measurement according to the recommendations of the Brighton collaboration and will be summarized according to the 3 schemes described below:

- by 0.5 °C increments: <36.0 , ≥ 36.0 - <36.5 , ≥ 36.5 - <37.0 , ≥ 37.0 - <37.5 , ≥ 37.5 - <38.0 , ≥ 38.0 - <38.5 , ≥ 38.5 - <39.0 , ≥ 39.0 - <39.5 , ≥ 39.5 - <40.0 , ≥ 40.0 °C
- by 1.0 °C increments: <36.0 , ≥ 36.0 - <37.0 , ≥ 37.0 - <38.0 , ≥ 38.0 - <39.0 , ≥ 39.0 - <40 , ≥ 40 °C

- $<38.0, \geq 38.0$ °C

Fever, defined as a body temperature of ≥ 38 °C irrespective of route of measurement, will be considered a systemic adverse event.

The analyses will encompass summaries of the data on five levels:

1. Daily reports of subjects with solicited adverse events.
2. Time of first onset of solicited adverse events (excluding 30 min post-vaccination).
3. Solicited adverse events, maximum event severity by event and time interval.
4. Number of days with solicited adverse events.
5. Solicited adverse events and indicators of solicited adverse events, occurrence of at least one event by category (local, systemic) and time interval.

For each of the time intervals presented in the summaries, only subjects with at least one plausible observation for the solicited adverse events will be included.

Level 1: Daily reports of solicited adverse event

For each time interval, only subjects with at least one plausible observation for the solicited adverse event will be included in the analysis. For each time interval, the number and percent of subjects will be presented by dosage group, solicited adverse event and overall.

Level 2: Time of first onset of solicited adverse events

The **time of first onset** of a solicited adverse event experienced by each subject is the time point at which the event first occurred. For erythema, induration and swelling, a threshold of ≥ 25 mm will be used. The summary will provide the frequencies and percentages of subjects with first onset of each solicited adverse events by dosage group and time point.

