For each dosage group, the first onset of the adverse event will be used for each subject.

Level 3: Solicited adverse events, maximum event severity by event and interval

The **maximum event severity** will be defined if there is at least one plausible observation within the time interval. Each subject's data will be aggregated across the time intervals and summarized according to the maximal severity observed for each adverse event,

followed by a summary across subjects for each dosage group. Subjects without any solicited adverse event data in the interval will be excluded from the analysis.

Level 4: Number of days with solicited adverse events

The number of days with the adverse event is defined irrespective of severity. This means at least ‘mild’ solicited adverse event that are assessed qualitatively and ≥ 25 mm for erythema, induration and swelling. If a solicited adverse event continues beyond day 14 the period after day 14 is added.

The frequency distribution of the number of days will be provided in a summary table by dosage group and adverse event.

Level 5: Solicited adverse events, occurrence of at least one event by category (local, systemic) and interval.

The **occurrence of at least one solicited adverse event** is defined as “any” for a subject who reports greater than “Grade 0” (≥ 25 mm for erythema, swelling and induration) for the respective event and “Grade 0” otherwise. The occurrence of at least one solicited adverse event (i.e., none versus any) will be summarized by category (i.e., local, systemic, any), by dosage group, and by time interval.

Medications to treat or prevent pain or fever will be summarized by frequencies and percentages of subjects reporting use of the medications by interval: 30 min, Days 1-4 (without 30 min), Days 5-8, Days 1-8 (without 30 min), Day 8-14, Days 1-14 (without 30 min).

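### The component intervals for solicited events, Days 5-8 and Days 8-14, share Day 8, so a reaction on that day alone is counted in two rows of the interval summaries.

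*SAP*

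**What the plan says.** SAP section 8.2.1 states that "the solicited study period (Days 1-14) after vaccination will be divided into these intervals". After the 30-minute reading it lists "Days 1-4 (without 30 min), Days 5-8, Days 1-8 (without 30 min), Days 8-14 and Days 1-14 (without 30 min"). The shared day sits in the run "Days 5-8, Days 1-8 (without 30 min), Days 8-14".

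The same pair of intervals appears in three more places:

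- Section 13.2, in the list of intervals for the separate analyses: "Days 1-4 (without 30 minutes), Days 5-8, Days 8-14, Days 1-8 (without 30 minutes) and Days 1-14 (without 30 minutes").
- Section 13.2, at the end, for medication to treat or prevent pain or fever: "Days 5-8, Days 1-8 (without 30 min), Day 8-14, Days 1-14 (without 30 min").
- Section 7.7, Table 7.7-1, where the solicited safety set has columns D5-D8 (flag SSS03FL) and D8-D14 (flag SSS04FL).

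Section 13.2 also fixes how a subject enters an interval. In general, "only subjects with at least one plausible observation for the solicited adverse events will be included". For Level 3, maximum severity "will be defined if there is at least one plausible observation within the time interval". Level 5 reports any event against none, also by interval.

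**The concern.** Where intervals divide a follow-up period, a reader takes each day to belong to one component. Here Day 8 belongs to two. A reaction confined to Day 8 then appears as an event of Days 5-8 and again as an event of Days 8-14, and its grade can set the maximum severity in both rows.

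At stake is how the time course of reactogenicity is read across the five dosage groups. Anyone comparing the two rows to see whether reactions persist would see one day of reaction as if it spanned two periods. Table 7.7-1 ties these safety sets to the primary safety objective. Section 14.1 uses safety data through Day 29 in the interim analysis for choosing an adjuvant dosage, so these summaries are within the material for that decision.

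**Working it through.** **Inputs**

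- Period: Days 1-14, 14 days (section 8.2.1).
- Component intervals: Days 1-4, 5-8 and 8-14 (sections 8.2.1, 13.2 and 7.7). Days 1-8 and Days 1-14 are left out because they are cumulative.
- Group size: 16 in each adjuvanted group, and 4 controls × 4 cohorts = 16 in the control group (section 3, Table 1).

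**Step 1: count the days.** Length = last day − first day + 1.

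| Scheme | Lengths | Sum | Days in two components |
|---|---|---|---|
| As written: 1-4, 5-8, 8-14 | 4 + 4 + 7 | 15 | Day 8 |
| Last interval from Day 9: 1-4, 5-8, 9-14 | 4 + 4 + 6 | 14 | none |
| Middle interval to Day 7: 1-4, 5-7, 8-14 | 4 + 3 + 7 | 14 | none |

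The plan's own total of 14 days is not reproduced by its components. The excess is 15 − 14 = 1 day-slot, which is Day 8.

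**Step 2: compare the other boundaries.** The 30-minute reading is taken out of Days 1-4. Days 1-4 are followed by Days 5-8. Section 8.2.1 ends the first unsolicited period at Day 14 and starts the next at Day 15. Only the Day 8 boundary overlaps.

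**Step 3: follow one subject.** Take a subject with complete data and a reaction on Day 8 only.

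| Row | Counted as having the event |
|---|---|
| Days 1-4 | no |
| Days 5-8 | yes |
| Days 8-14 | yes |
| Days 1-8 (cumulative) | yes, once |
| Days 1-14 (cumulative) | yes, once |

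A subject who reacts on, say, Days 6 and 10 properly appears in both component rows under any scheme. The fault is that a single day does so.

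**Step 4: weight of one subject.** With all 16 evaluable, 1/16 = 6.25 percentage points in each of the two rows.

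**Step 5: how often it could arise.** The SAP gives no frequency for reactions on Day 8 alone. If the true proportion in a group is p, the chance of at least one such subject among 16 is 1 − (1 − p)^16. For assumed values of p = 0.01, 0.05 and 0.10 this is 0.1485, 0.5599 and 0.8147. These equal the N = 16 column of Table 2 in SAP Addendum 1, section 2.1.

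**Step 6: outputs touched.** The double count reaches Level 3, Level 5 and the medication summary. It does not reach reports by single day, time of first onset (Level 2), number of days with an event (Level 4), or the cumulative rows. The Level 1 text mixes daily reports with time intervals. If that output is tabulated by interval instead of by day, the overlap applies there too.

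**The case against.** The overlap is stated the same way in four places. The sentence that speaks of dividing the period also lists two cumulative intervals, so it does not describe a strict partition. The row labelled Days 8-14 counts what its label says. The SAP sends details of solicited events to the protocol, which is not at hand, so the definition may be inherited. These points stand as reasons for caution about intent. They do not remove the overlap: no passage explains it or tells the reader that the components share a day.

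Three stronger readings are tempting, and the document does not support them:

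- **Second-week reactogenicity is inflated.** Section 8.7.3 makes the vaccination date Day 1, so Days 1-7 are the first week and Day 8 opens the second. A Day 8 reaction is a genuine second-week event.
- **The overlap distorts the late denominator.** A subject with only Day 8 data does enter both denominators. That comes mainly from the general rule that one plausible observation is enough. With Days 9-14, a subject with only Day 9 data would enter in the same way.
- **The tables are biased by 6.25 points.** That figure is the weight of one subject among 16, for any event in any row. The SAP does not say how many subjects would react on Day 8 alone, and the same intervals apply to all five groups.

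The remedy is also not unique. Days 5-7 with Days 8-14 would partition the period equally well.

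**Conclusion.** The point holds as a minor definitional error. Day 8 is the only day that falls in two component intervals. Following the plan as written places a reaction on that day alone in two rows of the interval-based descriptive summaries, with 6.25 percentage points per subject in each row when all 16 are evaluable. The conclusion assumes that the three component intervals were meant to be disjoint. Every other boundary in the safety section supports that, but the SAP does not say so outright.

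No hypothesis test or sample size depends on these intervals. A reader might infer that the primary safety comparison with control is compromised, and the document does not support that. The tables concerned are descriptive, the definition is common to all groups, and the by-day and cumulative outputs remain sound.

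**What to change.** Make the component intervals disjoint. The preferred change is Days 8-14 to Days 9-14 in section 8.2.1, in the interval list and the medication summary of section 13.2, and in the D8-D14 column of Table 7.7-1, with flag SSS04FL derived accordingly. The components then cover 14 days once each, and the last one starts where the cumulative Days 1-8 row ends.

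Check the boundary against the protocol first and align the two documents. If the overlap is deliberate, state that in section 8.2.1 and footnote the tables so that the rows are not read as disjoint.

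The cost is a text edit and one flag derivation. The small downside is that the last row would no longer start on the first day of the second week. Days 5-7 with Days 8-14 would keep that start, but the cumulative Days 1-8 row would then not end on a component boundary.

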8.2.2 Immunogenicity Data

Imputation methods will not be used. Primary, secondary, and exploratory objectives will be analyzed using the PPS. The primary objectives will also be analyzed using the FAS as a measurement of the robustness of the findings.

8.2.3 Efficacy Data

Not applicable.

8.3 Multicenter Studies

Not applicable.

8.4 Multiple Comparisons and Multiplicity

No multiple comparison adjustment will be performed.

8.5 Subsets

The B cell repertoire of the antigen specific B cells will be analyzed in a selected subset of subjects. This analysis is described in detail in a separate SAP Addendum for the exploratory endpoints.

8.6 Subgroups

Selected immunogenicity analyses may be provided based on seropositivity status at baseline.

8.7 Derived and Computed Variables

8.7.1 Demographics

Age is calculated in days for subjects using the following formula:

Age = Date of Visit 1 – Date of Birth + 1 (days) and

converted to years by dividing the resulting quantity by 365.25.

Body Mass Index (kg/m²) will be calculated using the following formula:

BMI = Weight (kg) / Height² (m²).

8.7.2 Immunogenicity

Values below the limit of quantification (recorded as “< LLQ”) will be set to half the lowest limit of quantification.

Titer greater or equal to a given threshold is defined as a binary variable for nonmissing values as:

= 1, if the titer is superior or equal to the given threshold (\geq 4-fold rise in hSBA titer),

= 0, otherwise.

Seroresponse is defined as a binary variable for subjects with non-missing values prevaccination and postvaccination as:

- For subjects with a prevaccination hSBA titer < 4:

= 1, if postvaccination titer \geq 8

- For subjects with a prevaccination hSBA titer ≥ 4 :

= 1, if post-vaccination titer increases at least 4 times the baseline hSBA titer

= 0, otherwise.

Geometric Mean Titer/Concentration

The GMT/GMC will be calculated using the following formula:

$$\text{GMT} = \sqrt[n]{t_1 t_2 \dots t_n} = \sqrt[n]{\log_{10}(t_1) + \log_{10}(t_2) + \dots + \log_{10}(t_n)} = 10^{\frac{1}{n} \sum_{i=1}^n \log_{10}(t_i)}$$

where t_1, t_2, \dots, t_n are n observed immunogenicity titers/concentrations.

Geometric Mean Ratio

Geometric mean ratios (GMRs) measure the changes in immunogenicity titers/concentrations *within* subjects.

The GMR will be calculated using the following formula:

$$\text{GMR} = \frac{\sqrt[n]{\log_{10}(v_{ij}) + \log_{10}(v_{ik})}}{\sqrt[n]{\log_{10}(v_{ij})}} = \frac{\sqrt[n]{\log_{10}(v_{ij}) + \log_{10}(v_{ik})}}{\sqrt[n]{\log_{10}(v_{ij})}} = 10^{\frac{1}{n} \sum_{k=1}^n \log_{10}(v_{ik}) - \frac{1}{n} \sum_{j=1}^n \log_{10}(v_{ij})}$$

where, for n subjects, v_{ij} and v_{ik} are observed immunogenicity titers/concentrations for subject i at time-points j and k , $j \neq k$.

8.7.3 Adverse Events

The time of onset of AEs is defined as:

Study day=Date of onset of AE – vaccination date + 1 (days).

Duration in the study is defined in days as:

Last visit date (visit x)^a– Enrollment date (visit 1) + 1 (days).

^a

or premature discontinuation date (in case of withdrawal from the study) The duration is missing if one of the dates is missing or incomplete.

Solicited Adverse Events

For details see [section 13.2](#).

Unsolicited Adverse Events

All adverse events will be characterized according to the date of occurrence related to the vaccination phase as follows:

- **Emergence before vaccination phase:** start date before the first date of injection of study vaccine.
- **Emergence during vaccination phase:** start date on or after the first date of injection of study vaccine or, adverse event increase in severity including to “serious” adverse event.

If start date is equal to the first date of injection, the “timing” variable (“On injection day, before injection”/“On injection day, after injection”) will be used to define whether the adverse event started before or after the injection.

If an adverse event start date is missing or unknown and the end date is not before the injection date, the adverse event will be considered as emergent.

When start and/or end dates of an adverse event are only partially known, adverse events will be categorized as emergent before and during vaccination phase using the following rules:

- If the partial end date is before (<) the first study vaccination (i.e., year or year & month is/are before the first study vaccination year or year & month), the adverse event is emergent before vaccination phase.

- If the partial start date is equal or after (\geq) the first study vaccination (i.e., year or year & month is/are after or the same as the first study injection year or year & month), the adverse event is emergent during vaccination phase.

The **maximum event severity** is the greatest severity associated with a system organ class/preferred term combination of an adverse event according to this order: Mild < Moderate < Severe. Unknown/ Missing severity is considered as severe (except for the definition of emergence).

Multiple AEs with the same PT for the same subject are counted only once when counting number of subjects with a given PT.

Vaccination-related Adverse Events are those for which the cause has been evaluated by the investigator, and recorded either as possibly related, probably related or unknown/ missing.

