8.7.5 Prior and Concomitant Medications

A **prior medication** is a medication used before the day of study vaccination (medication end date < study vaccination date).

A **post-vaccination medication** is a medication used only after study termination (i.e. medication start date > study termination date).

All other medications are **concomitant**.

When start and/or end dates of a medication intake are missing, the medication is considered as concomitant with the study vaccination schedule.

If the first study vaccination date is missing then the medication is considered as concomitant with the study vaccination schedule, provided that the study vaccine was administered to the subject.

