13.3 Unsolicited Adverse Events

All the unsolicited adverse events occurring during the study, judged either as probably related, possibly related, or not related to vaccination by the investigator, will be recorded.

The original verbatim terms used by investigators to identify adverse events in the Case Report Forms (CRFs) will be mapped to preferred terms using the MedDRA dictionary. The unsolicited adverse events will then be grouped by MedDRA preferred terms into frequency tables according to system organ class. All reported adverse events, as well as adverse events judged by the investigator as at least possibly related to study vaccine, will be summarized by dosage group, according to system organ class and preferred term within system organ class. When an unsolicited adverse event occurs more than once for a subject, the maximal severity and strongest relationship to the dosage group will be counted.

Only treatment-emergent adverse events will be analyzed, i.e., excluding those after a subject has given informed consent but before vaccination. The selection of unsolicited adverse events and the assignment to time intervals (Days 1-14 after vaccination, and from Day 15 post vaccination until study termination) will be done by day of onset and not by days ongoing/persisting.

The analysis of unsolicited adverse events comprises the following categories:

- Any unsolicited adverse event.
- Possibly or probably related unsolicited adverse events.
- Unsolicited adverse events leading to death.
- Serious adverse events.
- Possibly or probably related serious adverse event.
- Unsolicited adverse events leading to premature withdrawal from study.
- Medically attended adverse events.
- Adverse events of special interest (AESI).
- New onset of chronic disease (NOCD).

Data listings of all adverse events will be provided by subject. In addition, adverse events in the categories above will be provided as listed data.

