13.6 Concomitant Medication

The frequencies and percentages of subjects reporting concomitant medications will be tabulated overall and by dosage group. Medications (generic drug name) will be coded using the WHODRUG dictionary ([section 8.7.5](#) defines prior and concomitant medications).

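### The AE partial start-date rule and the medication missing-date rule override a known stop date before vaccination

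*SAP*

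**What the plan says.** Adverse events (SAP 8.7.3). The base definition places an event before or during the vaccination phase by its start date. Three further rules cover incomplete dates:

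- Start wholly missing. The event is emergent under the condition "If an adverse event start date is missing or unknown and the end date is not before the injection date". The end date is used.
- Partial end date. The bullet opens "If the partial end date is before (<) the first study vaccination", explained as an earlier year or year and month, and assigns the event to the phase before vaccination.
- Partial start date. The event is emergent during the vaccination phase when the "year or year & month is/are after or the same as the first study injection year or year & month". No end-date condition is attached.

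Medications (SAP 8.7.5). A prior medication is defined by its end alone: "medication end date < study vaccination date". A post-vaccination medication is defined by its start alone, namely a start after study termination. The missing-date sentence then reads: "When start and/or end dates of a medication intake are missing, the medication is considered as concomitant with the study vaccination schedule".

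Use of the classes. Section 8.2.1 says of unsolicited events that "these events will be reported from the date of signed informed consent to Day 14". Section 13.3 then restricts the analysis: "Only treatment-emergent adverse events will be analyzed, i.e., excluding those after a subject has given informed consent but before vaccination". Section 13.6 states: "The frequencies and percentages of subjects reporting concomitant medications will be tabulated overall and by dosage group".

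**The concern.** When a start date is uncertain, counting the event as emergent is a sensible cautious default. The uncertainty disappears, however, once a known end date shows that the event was over before the injection. The partial-start bullet keeps the default even then. The result is an odd ordering: knowing nothing about the start gives a better classification than knowing the month.

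The medication text has the same weakness and also contradicts itself, because the definition of prior does not need a start date while the missing-date sentence reclassifies the drug for lacking one.

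These cases can arise. Unsolicited events are collected from consent, and the Times and Events table (Table 3) places screening at Day -28 to -3, with unsolicited events and relevant medications assessed at that visit. At stake is that events which ended before the injection enter the treatment-emergent tables that serve the primary safety objective, and that stopped drugs enter the concomitant-medication table. Where two rules conflict, two programmers could also produce different tables from the same data.

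**Working it through.** The SAP gives no figure on this point, so there is none to reproduce. The check applies the rules literally.

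**Adverse events, vaccination on 15 March, complete end date 10 March**

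| Recorded start | Rule that applies | Class |
|---|---|---|
| 5 March (complete) | base definition | before vaccination |
| March, day unknown | partial start | emergent |
| vaccination year only | partial start | emergent |
| wholly missing | missing start, end checked | not made emergent |

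The event ended 15 − 10 = 5 days before the injection in every row, yet the class changes with how the start was recorded. The partial-end bullet does not help, because the end date is complete and lies in the vaccination month.

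**Adverse events, collision of the two bullets.** Take a year-only start in the vaccination year, a partial end of February and vaccination in March. The end bullet gives before vaccination, because February precedes March. The start bullet gives emergent, because the year is the same. The section states no precedence.

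**Medications**

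| Dates | By definition | By the missing-date sentence |
|---|---|---|
| End known, before vaccination; start missing | prior | concomitant |
| Start known, after study termination; end missing | post-vaccination | concomitant |

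**How far the AE rule reaches, given a partial date.** All events that start and end within the 28 days before vaccination were enumerated over 365 vaccination dates. Each date has 28 × 29 / 2 = 406 start-end pairs, so there are 365 × 406 = 148,190 cases. Assumptions: every pair is equally likely, the end date is complete, and the calendar year is arbitrary.

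- Start day missing: 55,622 / 148,190 = 37.5% classed emergent.
- Start known to the year only: 140,476 / 148,190 = 94.8%.
- Start wholly missing: 0 / 148,190 = 0%.

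If every event is instead assumed to end on the day before vaccination, the first two become 52.3% and 96.0%. These percentages are conditional on a partial start date being recorded. They show how often the rule errs when it is invoked; they do not estimate its effect on the tables.

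**Size per misplaced record.** Each LHD153R dosage group has 16 subjects, and the control group pools 4 × 4 = 16 (Table 1). One subject is 1/16 = 6.25 percentage points. This is a ceiling: section 8.7.3 counts a subject once per preferred term, so a misplaced event adds nothing to a row in which that subject already counts.

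**The case against.** The best reply is that the rules can be read sensibly. An event that ended on 10 March cannot have started on or after 15 March, so the base definition already settles it, and the partial-date bullets serve only where the order is undetermined. In the same way, a drug with a known end before vaccination already meets the definition of prior, and the missing-date sentence is for what the definitions cannot classify. That is probably the intent, but neither section says so. The partial-start bullet and the missing-date sentence are written without exception, and a program coded from them would misclassify.

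The reply is right about scope. A reader might infer that all the incomplete-date rules ignore the stop date. They do not: the AE rule for a wholly missing start uses it, although it leaves the pre-vaccination class implied rather than stated, and an earlier partial end date is addressed, though without precedence. For medications only the missing-date sentence is at fault, since 8.7.5 gives no partial-date rule.

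A reader might also take 6.25 points as the effect of every misplaced event, or suppose that unknown medication start dates are common enough to matter. The first is only a maximum, and the SAP offers nothing on the second. The AE case is narrow as well: the event must begin and end before the injection, have a partial start date in the vaccination month or year, and have an end date that the end bullet does not settle.

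**Conclusion.** The point holds for two rules, the AE partial start-date bullet in 8.7.3 and the medication missing-date sentence in 8.7.5. Both are wrong as written, because they assign a class that a known date rules out. In addition, the two AE bullets can give opposite answers with no precedence.

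The error runs one way, towards too many emergent events and too many concomitant medications. It can fall in the control group as well as in an LHD153R group, so the direction of its effect on a between-group comparison is not fixed. The size is at most 6.25 percentage points per misplaced record in a row for a 16-subject group, and often zero. The number of such records is not given in the SAP; that they are rare is a judgement. Nothing in the document suggests that a study conclusion would change, and the medication table is descriptive. The importance is low, and the case for the change rests on its negligible cost.

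**What to change.** In 8.7.3, state that a complete or partial end date which establishes that the event ended before vaccination takes precedence over the start-date rules and makes the event pre-vaccination. This removes the misclassification, resolves the collision of the two bullets, and makes explicit what the missing-start rule only implies. Under it, none of the 148,190 enumerated cases would be flagged emergent.

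In 8.7.5, state three things in order:

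1. A medication with a known end date before vaccination is prior, whatever its start date.
2. A medication with a known start date after study termination is post-vaccination, whatever its end date.
3. Only medications that the available dates cannot classify default to concomitant.

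The second line is needed. A correction of the prior class alone would leave the mirror error for drugs started after termination with a missing end date.

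The cost is a few sentences in the SAP and the matching conditions in the two derivation programs. No data collection changes.
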